4.4 Step 2 Exclusion Criteria

NOTE: Below exclusion criteria apply to the following groups of participants:

- Participants transitioning directly from Step 1 to Step 2 as part of A5354 Version 2.0.

OR

- Participants enrolling to Step 2 after having previously completed the week 72 visit and who went off study under A5354 Version 1.0.

- 4.4.1 ARV interruption for greater than or equal to 7 consecutive days at any time after ART initiation and prior to entry into Step 2, including while on Step 1 or after completion of Step 1.

- 4.4.2 Protocol-defined virologic failure ([section 6.3.4](#)) at any time prior to entry into Step 2, including while on Step 1 or after completion of Step 1.**
 - 4.4.3 Active drug or alcohol use or dependence that, in the opinion of the site investigator, would interfere with adherence to study requirements.**
 - 4.4.4 Any acute, chronic, or recent and clinically significant medical condition that, in the opinion of the site investigator, would interfere with adherence to study requirements or jeopardize the safety or rights of the participant.**
 - 4.4.5 Receipt of any investigational study agent since entry to Step 1.**
 - 4.4.6 Chronic or recurrent use of medications that modify the host immune response (e.g., oral or parenteral steroids, cancer chemotherapy, biologics).**
- 4.5 Study Enrollment Procedures**
- 4.5.1** Prior to implementation of this protocol, and any subsequent full version amendments, each site must have the protocol and the protocol consent form approved, as appropriate, by their local institutional review board (IRB)/Ethics Committee (EC) and any other applicable regulatory entity (RE). Upon receiving final approval, sites will submit all required protocol registration documents to the DAIDS Protocol Registration Office (DAIDS PRO) at the Regulatory Support Center (RSC). The DAIDS PRO will review the submitted protocol registration packet to ensure that all of the required documents have been received.
- Site-specific informed consent forms (ICFs) WILL be reviewed and approved by the DAIDS PRO, and sites will receive an Initial Registration Notification from the DAIDS PRO that indicates successful completion of the protocol registration process. A copy of the Initial Registration Notification should be retained in the site's regulatory files.
- Upon receiving final IRB/EC and any other applicable RE approval(s) for an amendment, sites should implement the amendment immediately. Sites are required to submit an amendment registration packet to the DAIDS PRO at the RSC. The DAIDS PRO will review the submitted protocol registration packet to ensure that all the required documents have been received. Site-specific ICF(s) WILL NOT be reviewed and approved by the DAIDS PRO and sites will receive an Amendment Registration Notification when the DAIDS PRO receives a complete registration packet. A copy of the Amendment Registration Notification should be retained in the site's regulatory files.

For additional information on the protocol registration process and specific documents required for initial and amendment registrations, refer to the current version of the DAIDS Protocol Registration Manual

(<https://rsc.niaid.nih.gov/clinical-research-sites/daids-protocol-registration-policy-and-procedures-manual>).

Once a candidate for study entry has been identified, details will be carefully discussed with the participant. The participant will be asked to read and sign the approved protocol consent form.

Participants from whom a signed informed consent has been obtained may be screened and enrolled, if they otherwise qualify. An ACTG Screening Checklist must be entered through the DMC Participant Enrollment System.

4.5.2 Protocol Activation

Prior to enrollment, sites must complete the Protocol Activation Checklist found on the ACTG Member website. This checklist must be approved prior to any screening of participants for enrollment.

4.5.3 Participant Registration

For candidates from whom informed consent has been obtained, but who are deemed ineligible or who do not enroll into the initial protocol step, an ACTG Screening Failure Results form must be completed and keyed into the database. Participants who meet the enrollment criteria will be registered to the study according to standard ACTG DMC procedures.

4.6 Coenrollment Guidelines

- US sites are encouraged to coenroll participants in A5128, “Plan for Obtaining Informed Consent to Use Stored Human Biological Materials (HBM) for Currently Unspecified Analyses.”
- Non-US sites are encouraged to coenroll participants in A5243, “Plan for Obtaining Human Biological Samples at Non-US Clinical Research Sites for Currently Unspecified Genetic Analyses.”
- Coenrollment in A5128 or A5243 does not require permission from the A5354 protocol chairs.
- For specific questions and approval for coenrollment in other studies, sites should contact the protocol team via e-mail as described in the [Study Management section](#).

5.0 STUDY TREATMENT

5.1 Regimens, Administration, and Duration

Study treatment is defined as STR elvitegravir/cobicistat/emtricitabine/tenofovir alafenamide (EVG/COBI/FTC/TAF) **or bictegrovir/emtricitabine/tenofovir alafenamide (BIC/FTC/TAF)**, which will be provided through the study.

NOTE: Switching of ARV regimen is allowed (i.e., from EVG/COBI/FTC/TAF to BIC/FTC/TAF, or vice versa, or to an alternate non-study-provided ART) without consulting the CMC.

5.1.1 Regimen

Participants will receive elvitegravir 150 mg/cobicistat 150 mg/emtricitabine 200mg/tenofovir alafenamide 10mg (EVG/COBI/FTC/TAF) **or bictegrovir 50mg/emtricitabine 200 mg/tenofovir alafenamide 25 mg (BIC/FTC/TAF).**

NOTE: Other non-study-provided ARV regimens will be allowed for participants who are pregnant, breastfeeding, or unable/unwilling to take EVG/COBI/FTC/TAF **or BIC/FTC/TAF**, or for participants whose local health care/primary care provider prefers starting a different initial ARV regimen.

5.1.2 Administration

EVG/COBI/FTC/TAF **(with food)** or BIC/FTC/TAF **(with or without food)** will be administered as one tablet by mouth daily.

5.1.3 Duration

On Step 1, participants will take study medications for up to **72** weeks.

On Step 2, participants will take study medications for up to **144** weeks.

5.2 Study Product Formulation and Preparation

EVG/COBI/FTC/TAF **and BIC/FTC/TAF** tablets. Store at 25°C (77°F); excursions permitted from 15-30°C (59°-86°F); USP Controlled Room Temperature.

5.3 Pharmacy: Product Supply, Distribution, and Accountability

5.3.1 Study Product Supply/Distribution

EVG/COBI/FTC/TAF **and BIC/FTC/TAF** will be supplied by Gilead.

EVG/COBI/FTC/TAF **and BIC/FTC/TAF** will be available through the NIAID Clinical Research Products Management Center (CRPMC). The site pharmacist

should obtain the study product(s) for this protocol by following the instructions in the manual *Pharmacy Guidelines and Instructions for DAIDS Clinical Trials Networks*.

Any study product not provided by the study must comply with the NIAID (DAIDS) policy that outlines the process for authorizing the use of study products not marketed in the US in NIAID (DAIDS)-supported and/or -sponsored clinical trials. This policy is available on the NIAID (DAIDS) website at <https://www.niaid.nih.gov/sites/default/files/NonFDAapprovedProducts.pdf>.

5.3.2 Study Product Accountability

The site pharmacist is required to maintain complete records of all study products received from the NIAID CRPMC and subsequently dispensed. At US CRSs, all unused study products must be returned to the NIAID CRPMC (or as otherwise directed by the sponsor) after the study is completed or terminated. The procedures to be followed are provided in the manual *Pharmacy Guidelines and Instructions for DAIDS Clinical Trials Networks*. At non-US CRSs, the site pharmacist must follow the instructions in the *Pharmacy Guidelines and Instructions for DAIDS Clinical Trials Networks* for the destruction of unused study products.

5.4 Concomitant Medications

Whenever a concomitant medication or study agent is initiated or a dose changed, investigators must review the concomitant medication's and study agent's most recent package insert, Investigator's Brochure, or updated information from DAIDS to obtain the most current information on drug interactions, contraindications, and precautions.

Additional drug information may be found on the updated ACTG Drug Interactions Database located at http://tprc.pharm.buffalo.edu/home/di_search/.

5.4.1 Required Medications

Participants must be on a combination ARV regimen. The study-provided regimen will be STR EVG/COBI/FTC/TAF or **BIC/FTC/TAF**. EVG/COBI/FTC/TAF or **BIC/FTC/TAF**, but alternative regimens are allowed based on clinical indication or participant preference ([section 5.1.1](#)). **Switching of ARV regimens is allowed (e.g., from EVG/COBI/FTC/TAF to BIC/FTC/TAF or to an alternate non-study-provided ART) without consulting the CMC.**

5.4.2 Prohibited Medications

Table 5.4.2-1: Prohibited Medications for EVG/COBI/FTC/TAF

Medication/Drug Class	Prohibited Medication
Anti-infectives	Any anti-HIV combination drugs containing FTC or lamivudine such as 
 • Atripla (efavirenz, emtricitabine, and tenofovir); • Combivir (lamivudine and zidovudine); • Complera (rilpivirine, emtricitabine, and tenofovir); • Epivir (lamivudine); • Epzicom (abacavir and lamivudine); • Stribild (cobicistat, elvitegravir, emtricitabine, and tenofovir); • Trizivir (abacavir, lamivudine, and zidovudine); and • Truvada (emtricitabine and tenofovir).
Concomitant use with Tybost and atazanavir or darunavir AND any of the following drugs listed below:	
Alpha 1-Adrenoreceptor Antagonist	
 • Alfuzosin
Antiarrhythmic	
 • Dronedarone
Anti-bacterial	
 • Rifamycins (rifampin, rifabutin, rifapentine)
Anti-infectives	Any anti-HIV drugs containing tenofovir: 
 • Atripla; • Complera; • Descovy • Odefsey • Stribild; and • Symtuza • Truvada In combination with HEPSERA
Antimicrobial	
 • Rifampin
Antineoplastics	
 • Irinotecan
Ergot Derivatives	
 • Dihydroergotamine, • Ergotamine, • Methylergonovine
GI Motility Agent	
 • Cisapride
Herbal Products	
 • St. John's wort (Hypericum perforatum)
HMG-CoA Reductase Inhibitors	
 • Lovastatin, • Simvastatin
Nephrotoxic drugs	
 • Cidofovir • Hepsera (adefovir)
Non-nucleoside Reverse Transcriptase Inhibitor	
 • Nevirapine
Phosphodiesterase-5	
 • Sildenafil when administered as Revatio for the treatment of

Medication/Drug Class	Prohibited Medication
(PDE5) Inhibitor	pulmonary arterial hypertension
Protease Inhibitor	
 • Indinavir
Sedative/Hypnotics	
 • Triazolam, chronic oral midazolam (one oral dose permitted)
Due to the need to use Vitekta with a protease inhibitor coadministered with ritonavir, consult prescribing information of coadministered protease inhibitor and ritonavir for their contraindications.	
Anti-infectives	
 • Any anti-HIV drugs containing elvitegravir: • Stribild

Table 5.4.2-2: Prohibited Medications for BIC/FTC/TAF

Medication/Drug Class	Prohibited Medication
Antiarrhythmic Agent	Dofetilide
Anticonvulsants	
 • carbamazepine • oxcarbazepine • phenobarbital • phenytoin
Antimycobacterials	
 • rifabutin • rifampin • rifapentine
Antiretrovirals	
 • Any antiretroviral drug that is not part of the study regimen
Herbal/Natural Supplements	
 • St. John's Wort

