
The following ARVs are not recommended in combination with Tybost because dosing recommendations for such combinations have not been established, and co-administration may result in decreased plasma concentrations of the ARV agents, leading to loss of therapeutic effect and development of resistance:
 
 • More than one ARV that requires pharmacokinetic enhancement (i.e., two protease inhibitors or a protease inhibitor in combination with elvitegravir) • Atazanavir in combination with efavirenz in treatment-experienced patients • Atazanavir in combination with etravirine • Darunavir 600 mg twice daily • Darunavir in combination with efavirenz, nevirapine, or etravirine • Other HIV-1 protease inhibitors including fosamprenavir, saquinavir, or tipranavir • Tybost in combination with Stribild fixed-dose combination tablets (elvitegravir, cobicistat, emtricitabine, tenofovir DF) is not recommended because cobicistat is a component of Stribild. • Tybost in combination with lopinavir/ritonavir or regimens containing ritonavir is not recommended due to similar effects of Tybost and ritonavir on CYP3A. 	

Table 5.4.3-2: Precautionary Medications for BIC/FTC/TAF

Medication/Drug Class	Precautionary Medications
Medications or oral supplements containing polyvalent cations (e.g., Mg, Al, Ca, Fe): Calcium or iron supplements Cation-containing antacids or laxatives Buffered medications	
 • Antacids containing Al/Mg or Calcium: • BIKTARVY and supplements containing calcium or iron can be taken together with food. Routine administration of BIKTARVY under fasting conditions simultaneously with, or 2 hours after, supplements containing calcium or iron is not recommended. • BIKTARVY can be taken under fasting conditions 2 hours before antacids containing Al/Mg or calcium. • Routine administration of BIKTARVY simultaneously with, or 2 hours after, antacids containing Al/Mg or calcium is not recommended. • Supplements containing Calcium or Iron:
Hypoglycemic agent	
 • Metformin. Refer to the prescribing information of metformin for assessing the benefit and risk of concomitant use of BIKTARVY and metformin.

Evaluation	Screening	Step 1 Entry	1	2 (section 6.3.3)	4	8 (section 6.3.3)	12	24 (section 6.3.3)	36	48	49 (optional, section 6.4.8)	60	72	Virologic Failure Confirmation	Premature Study/ Treatment Discontinuation

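### The prohibited-drug table for EVG/COBI/FTC/TAF ties all 12 of its non-antiretroviral rows to atazanavir or darunavir, which that tablet does not contain

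*Protocol*

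**What the plan says.** Section 5.4.2 gives a separate list for each study-provided regimen. The first is titled "Table 5.4.2-1: Prohibited Medications for EVG/COBI/FTC/TAF" and is built as follows:

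- One row of antiretroviral combination products containing emtricitabine (FTC) or lamivudine.
- A sub-header: "Concomitant use with Tybost and atazanavir or darunavir AND any of the following drugs listed below".
- Fifteen rows of drug classes in alphabetical order, from the alpha-1 antagonist row to the sedative/hypnotic row.
- A note beginning "Due to the need to use Vitekta with a protease inhibitor coadministered with ritonavir", followed by one row of products containing elvitegravir.

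Section 5.1.1 defines the regimen as elvitegravir, cobicistat, emtricitabine and TAF. Section 5.1.2 says that it "will be administered as one tablet by mouth daily".

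The second list, "Table 5.4.2-2: Prohibited Medications for BIC/FTC/TAF", has no sub-header and no condition.

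Section 5.4 also requires investigators to review the current package insert, Investigator's Brochure or sponsor updates whenever a concomitant drug or study agent is started or its dose changed, "to obtain the most current information on drug interactions, contraindications, and precautions". Section 9.1 lists the need for a prohibited concomitant medication as a reason for stopping study drug early, and refers to section 5.4 as a whole.

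**The concern.** The title and the sub-header give different rules. The title says the drugs are prohibited with the tablet. The sub-header says the rows below it apply when the participant is also taking atazanavir or darunavir, and the tablet contains neither.

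This list is operative safety text. Sites use it to decide what may be given alongside study drug, and section 9.1 attaches a consequence to it. Section 5.1 lets participants switch between the two study regimens without consulting the Clinical Management Committee, so sites use both tables side by side. One bars rifamycins and St. John's wort outright; the other, read as written, does not bar them for a participant on the tablet. Rifamycins are not a remote case, because section 6.4.4 requires any history of tuberculosis to be recorded whenever it was diagnosed.

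The stake is participant safety and consistent conduct across sites. The comparison of Fiebig groups on cell-associated HIV-1 DNA is not in question.

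**Working it through.** There is no figure in the plan to reproduce. The check is a reading of the condition against the regimen, followed by a count of rows.

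**Does the tablet meet the condition?** The sub-header can be parsed as Tybost together with either atazanavir or darunavir, or as Tybost with atazanavir on one side and darunavir alone on the other. Both readings need one of the two protease inhibitors. Section 5.4.3 implies that Tybost is cobicistat: adding it to Stribild "is not recommended because cobicistat is a component of Stribild". So the tablet supplies at most the cobicistat part of the condition. A participant on the tablet would have to add atazanavir or darunavir to meet it, and Table 5.4.3-1 itself advises against combining a protease inhibitor with elvitegravir on top of Tybost.

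**Rows under the sub-header, with the number of named entries in each:**

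| Row | Entries | Antiretroviral? |
|---|---|---|
| Alpha-1 antagonist | 1 | no |
| Antiarrhythmic | 1 | no |
| Anti-bacterial (rifamycins) | 3 | no |
| Anti-infectives (tenofovir products) | 7 | yes |
| Antimicrobial (rifampin) | 1 | no |
| Antineoplastic | 1 | no |
| Ergot derivatives | 3 | no |
| GI motility | 1 | no |
| Herbal (St. John's wort) | 1 | no |
| HMG-CoA reductase inhibitors | 2 | no |
| Nephrotoxic drugs | 2 | no |
| Non-nucleoside inhibitor (nevirapine) | 1 | yes |
| PDE5 inhibitor | 1 | no |
| Protease inhibitor (indinavir) | 1 | yes |
| Sedative/hypnotics | 2 | no |

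- Conditional rows: 15. Antiretroviral among them: 3. Non-antiretroviral: 15 − 3 = 12.
- Conditional entries: 1+1+3+7+1+1+3+1+1+2+2+1+1+1+2 = 28. Antiretroviral among them: 7+1+1 = 9. Non-antiretroviral: 28 − 9 = 19, with rifampin counted twice.
- Rows outside the condition: 2 (FTC/lamivudine products with 8 entries, elvitegravir products with 1), so 9 entries, all antiretroviral.
- Whole table: 15 + 2 = 17 rows and 28 + 9 = 37 entries.

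So 15 of 17 rows and 28 of 37 entries are conditional, and these include every non-antiretroviral row (12 of 12) and entry (19 of 19).

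**How far does the sub-header reach?** The count assumes that it runs down to the Vitekta note. The 15 rows form one alphabetical sequence between those two markers, which supports that. If it stopped instead at the page break inside the PDE5 row, the last two rows (protease inhibitor, sedative/hypnotics) would drop out. That leaves 15 − 2 = 13 of 17 rows, and 12 − 1 = 11 of 12 non-antiretroviral rows.

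**Comparison with the other regimen.** Table 5.4.2-2 has 5 rows, 4 of them non-antiretroviral, and none is conditional. Rifabutin, rifampin, rifapentine and St. John's wort appear in both tables.

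**Later changes.** The section lists of the two letters of amendment do not include 5.4.2. The visible part of the clarification memo does not touch it either, but that memo is only partly reproduced in the material reviewed.

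**The case against.** The best case for leaving the table alone has four parts.

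1. **The intent is clear.** The section heading, table title and column heading all say prohibited. A site looking up rifampin finds it under all three and would have to let one sub-header override them. The documents show no site doing so. This is probably how most readers would take the table. It supports correcting the sub-header, since a safety list should not depend on sites ignoring its own stated condition.

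2. **The wording may have a purpose.** Section 8.0 allows individual component formulations, with a drug substitution, after treatment-limiting toxicity from the single tablet, and non-study regimens are permitted throughout. Text about Tybost and Vitekta as separate products could serve those cases. This may explain where the wording came from, but it supplies no rule for a participant on the tablet alone, which is what the title promises.

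3. **The package-insert review covers the risk.** It is mandatory at each start or dose change and is a real safeguard. It tells the investigator what the label says. It does not say which drugs the protocol prohibits for the purposes of section 9.1.

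4. **The scope of the sub-header is uncertain.** Some rows fit a protease-inhibitor condition poorly: the tenofovir products tied to Hepsera, the cidofovir/adefovir row, and rifampin listed twice. Several component lists may have been merged. That uncertainty stands, and it is why the protocol team should decide which rows apply.

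**Conclusion.** The concern holds. As written, the table's title and its sub-header contradict each other. On a literal reading, only duplicate antiretrovirals (FTC/lamivudine products and elvitegravir products) are barred for a participant on the EVG/COBI/FTC/TAF tablet, and none of the listed non-antiretroviral drugs is.

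The exact counts rest on the sub-header extending to the Vitekta note and on classing the cidofovir/adefovir row as non-antiretroviral. The narrower reach, to the page break, changes the size slightly and leaves the conclusion the same.

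This is an inconsistency of wording in a safety table. It should be corrected, but its practical weight is moderate because of the label review. No harm has been shown, and the number of participants exposed cannot be derived from the documents.

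**What to change.** Issue a clarification memo for Table 5.4.2-1 that deletes the sub-header or replaces it with wording such as: *Concomitant use of EVG/COBI/FTC/TAF with any of the following drugs is prohibited.* Before it goes out, the protocol team should check each row against the current label for the single tablet and confirm which apply. If some rows are meant only for component products used with a protease inhibitor, move them to a separately titled table.

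The cost is one memo and the rewording of one table row. Visits, data collection and analysis are unchanged.

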5.4.3 Precautionary Medications

Package inserts or investigator brochures for ARV drugs and concomitant agents and updated information from the DAIDS should be consulted whenever a concomitant medication is initiated or a dose is changed. Additional drug information may be found in the ACTG Drug Interaction Database on the ACTG website at: <https://actgnetwork.org/ACTG-Drug-Interactions-Database>.

Table 5.4.3-1: Precautionary Medications for EVG/COBI/FTC/TAF

- | |
|---|
| 
 • Take caution when used in patients with known risk factors for liver diseases and impaired renal function. • Reduction of the dosage of Emtriva is recommended for patients with impaired renal function. • Take caution when used in patients at risk for renal dysfunction and/or who have new onset or worsening renal impairment. |
|---|

 • Take caution when used in combination with a protease inhibitor and cobicistat. 	
Anticoagulants Antifungals Anti-inflammatory	Colchicine Rivaroxaban Voriconazole

 • Take caution when used in patients with medical conditions (e.g., new onset or worsening renal impairment) or who are receiving drugs needing monitoring with estimated creatinine clearance. • Coadministration of Tybost and tenofovir DF is not recommended in patients who have an estimated creatinine clearance below 70 mL/min because dose adjustment of tenofovir DF is required below 50 mL/min and such dose adjustments have not been established for coadministration with Tybost. • Coadministration of Tybost and tenofovir DF in combination with concomitant or recent use of a nephrotoxic agent is not recommended. 	

The following ARVs are not recommended in combination with Tybost because dosing recommendations for such combinations have not been established, and co-administration may result in decreased plasma concentrations of the ARV agents, leading to loss of therapeutic effect and development of resistance:
 
 • More than one ARV that requires pharmacokinetic enhancement (i.e., two protease inhibitors or a protease inhibitor in combination with elvitegravir) • Atazanavir in combination with efavirenz in treatment-experienced patients • Atazanavir in combination with etravirine • Darunavir 600 mg twice daily • Darunavir in combination with efavirenz, nevirapine, or etravirine • Other HIV-1 protease inhibitors including fosamprenavir, saquinavir, or tipranavir • Tybost in combination with Stribild fixed-dose combination tablets (elvitegravir, cobicistat, emtricitabine, tenofovir DF) is not recommended because cobicistat is a component of Stribild. • Tybost in combination with lopinavir/ritonavir or regimens containing ritonavir is not recommended due to similar effects of Tybost and ritonavir on CYP3A. 	

Table 5.4.3-2: Precautionary Medications for BIC/FTC/TAF

Medication/Drug Class	Precautionary Medications
Medications or oral supplements containing polyvalent cations (e.g., Mg, Al, Ca, Fe): Calcium or iron supplements Cation-containing antacids or laxatives Buffered medications	
 • Antacids containing Al/Mg or Calcium: • BIKTARVY and supplements containing calcium or iron can be taken together with food. Routine administration of BIKTARVY under fasting conditions simultaneously with, or 2 hours after, supplements containing calcium or iron is not recommended. • BIKTARVY can be taken under fasting conditions 2 hours before antacids containing Al/Mg or calcium. • Routine administration of BIKTARVY simultaneously with, or 2 hours after, antacids containing Al/Mg or calcium is not recommended. • Supplements containing Calcium or Iron:
Hypoglycemic agent	
 • Metformin. Refer to the prescribing information of metformin for assessing the benefit and risk of concomitant use of BIKTARVY and metformin.

Evaluation	Screening	Step 1 Entry	1	2 (section 6.3.3)	4	8 (section 6.3.3)	12	24 (section 6.3.3)	36	48	49 (optional, section 6.4.8)	60	72	Virologic Failure Confirmation	Premature Study/ Treatment Discontinuation
	-7 days	day 0	± 3 days		±7 days		±14 days		-14 days to +3 days	-3 days to +14 days	± 42 days				
Pregnancy Testing (section 6.4.7)		X	If sus- pected		If sus- pected		Whenever pregnancy is suspected								X
CD4+/CD8+ T-cells		X					X	X		X		X	X	X	X
PBMC and Plasma Storage		X (section 6.4.8)			X		X (section 6.4.8)	X (section 6.4.8)		X	If needed	X (section 6.4.8)	X (section 6.4.8)		
Plasma HIV-1 RNA (section 6.4.9)		X			X		X	X	X	X		X	X	X	X
HIV-1 Genotype (section 6.4.9)		X												X	
Total HIV-1 DNA by qPCR (section 6.4.9)		X								X	If needed				
Telephone Evaluations (section 6.3.3)				X		X							X		
Adherence Assessment and Counseling			X		X		X	X	X	X		X	X	X	
Consent for Optional Procedures and Large Volume Blood Collection (after week 48; section 6.4.11)		X											X		
Leukapheresis (optional as an alternative to large volume blood draw; (section 6.4.11)		X													
Gut Biopsy (optional; section 6.4.11)													X		
Lumbar Puncture (optional; section 6.4.11)													X		

6.2 SOE for Step 2

Table 6.2-1: Step 2 SOE

Evaluation	Step 2 Registration	Post-Step 2 Registration Evaluations (Weeks)	Virologic Failure Confirmation	Premature Study/Treatment Discontinuation
		Q24 (24, 48, 72, 96, 120, and 144)		
	Day 0	± 60 days		
Clinical Assessment	X	Q24		X
Complete Physical Exam	X			X
Targeted Physical Exam		Q24		
Weight	X	Q24		X
Confirmation of ART Continuation	X	Q24		
ART Modifications	X	Q24	X	X
Hematology, Chemistries, Liver Function Tests	X	Q24 (perform if needed, section 6.4.7)		X
Pregnancy Testing (section 6.4.7)	X	Whenever pregnancy is suspected		X
CD4+/CD8+ T-cells	X	Q48 (record results from routine care, section 6.4.8)		
Plasma HIV-1 RNA (section 6.4.9)	X	Q24	X	X
Adherence Assessment	X	Q24	X	

